With the subject's permission we may photograph or videotape the procedures described above for educational, training, or publication purposes. The photos or video will focus only on the lead insertion site and affected limb. Ultrasound images from the procedure may also be collected. Every effort will be made to protect the subject's privacy and the photos or video will not include the subject's face or any other personal identifiers such as birthmarks. Subjects and their caretakers will be trained in device care and management, and given written instructions as well. Following successful lead insertion, a perineural catheter may be inserted, if the patient desires a catheter (with normal saline injection and not local anesthetic via the inserting needle). This will be used to deliver perineural local anesthetic as a rescue analgesic method postoperatively in case the SPRINT system provides inadequate analgesia.

Randomization. Within the recovery room, the surgeon often performs a standard neurologic examination (variable depending on the surgeon and surgical procedure), after which time the subject will have baseline end points measured, including a pain score at the surgical site using the Numeric Rating Scale (NRS, 0-10), pain score (NRS) within the target nerve distribution, and

sensory deficits (measured with alcohol pads and von Frey filament, compared to the contralateral limb within the cutaneous distribution of the target nerve). For their first pulse generator—“Stimulator A”—subjects will be randomized to one of two treatments—current or sham—using computer generated lists and opaque, sealed envelopes. The stimulator will then be attached to the lead and switched “on” (sham stimulator produces no current). The end points will be measured per the table below. Subsequently, the stimulator will be replaced by the alternative (current or sham)—“Stimulator B”. The subject will have the end points measured and the stimulator replaced with a unit set to deliver active current for the remainder of study participation (“Stimulator C”). Operating and recovery room pharmacologic analgesic requirements will be recorded. Of note, if a lead fails to provide paresthesias within the target nerve distribution with either Stimulator A or B (adjustment of stimulator settings allowed), the lead may be replaced at the discretion of the subject and investigators.

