Of note, the data derived from the chronic pain literature suggests that there is a “carry over” effect following stimulation: analgesia is provided even after the cessation of electrical current. It remains unknown if this is true following surgery in the acute postoperative pain period. For subjects randomized to active current from Stimulator A, the data collected for Stimulator B placebo treatment may be lowered due to the carry over effect. Therefore, this data will not be compared with the baseline or Stimulator A outcome measures. However, it is valuable data to possibly detect and quantify the carry-over effect of the initial stimulation.

At any time, subjects may choose to have their perineural catheter bolused with local anesthetic and a perineural local anesthetic infusion begun (if they desired a catheter with subsequent insertion). Therefore, subjects will not risk receiving inferior analgesia by participating in this study. However, subjects also have the option of leaving their infusion pump off and using neuromodulation as their primary analgesic if the latter proves adequate—the decision is completely each subject’s and may be made any time prior to perineural catheter removal.

Subjects and their caretakers will be trained in device care and management, and given written instructions as well. Pain scores (resting and dynamic worst and average) will be collected daily for two weeks, along with oral analgesic requirements, perineural local anesthetic use, and sensory/motor deficits (all specific to the previous 24 hours). Perineural catheters will be removed at home upon subject request, after 3 days, or upon local anesthetic reservoir exhaustion, whichever comes first (standard-of-care). The electrical leads will be removed upon subject request, or after 30 days, whichever comes first. The leads will be removed at home by subjects or their caretakers (standard-of-care for perineural catheter withdrawal) or by investigators, depending on both investigator and subject preference. If removed by subjects or their caretakers, a picture of the extracted lead tip must be texted/mailed to investigators, or the physical lead returned to investigators for inspection. Subjects will be contacted no less than every 5 days following the initial 2-week period until their lead is removed; and, will then be contacted 1 and 3 months postoperatively and the end points again verbally collected.

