Sample Size Estimation and Statistical Analysis Plan. This is a feasibility study to demonstrate proof-of-concept and generate data to help design and power subsequent definitive, randomized, controlled clinical trials. Therefore, a convenience sample of 40 subjects will be enrolled (10 additional subjects permitted to account for any drop-outs for a total of 50 subjects). Although this is a feasibility—and not definitive—investigation, we will treat as the primary end point the difference between the baseline pain score and pain score 5 minutes after the active (non-sham) electrical stimulator is first turned on.

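### The primary end point is an uncontrolled before-after change over an interval that differs by sequence, and the randomized sham in Stimulator A has no role in it

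*Combined protocol and SAP*

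**What the plan says.** Under Randomization, after the surgeon's examination in the recovery room, "the subject will have baseline end points measured, including a pain score at the surgical site". Stimulator A is then allocated at random as current or sham, attached and switched on; the same section states that the "sham stimulator produces no current". Of the measurements on Stimulator A it says "The end points will be measured per the table below"; that timing table is not in the available text. Stimulator B is whichever unit was not used first, and end points are measured again. No second baseline is described, and no allocation ratio is given. The section adds: "Operating and recovery room pharmacologic analgesic requirements will be recorded".

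The text on carry-over contains the only sequence-specific rule. In subjects who had current first, the later sham data are kept out of comparisons with baseline and Stimulator A. The next paragraph says "At any time, subjects may choose to have their perineural catheter bolused with local anesthetic"; the catheter itself is optional.

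The Sample Size Estimation and Statistical Analysis Plan sets a convenience sample of 40 (up to 50 with drop-outs). It calls the study feasibility rather than definitive, and says the data should help in designing and powering later randomized controlled trials. The primary end point is baseline pain against the "pain score 5 minutes after the active (non-sham) electrical stimulator is first turned on". No test, sequence term or sham comparison is stated for it.

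**The concern.** One definition covers two different intervals, and neither has a comparator. A fall in pain from baseline to active stimulation contains the device effect plus whatever else happened in that time: response to being treated, recovery-room analgesics, regression to the mean, or a rise in pain as intraoperative analgesia wears off. Sham-first subjects have more time, a sham exposure and more opportunity for analgesia before their primary score.

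What is at stake is the planning use. A later sham-controlled trial needs the device-versus-sham difference. If the pooled change is carried forward as that difference, the later trial could be too small (non-specific relief counted as device effect) or a useful device could look weak (rising pain counted against it). The trial already randomizes sham in the first period, so a controlled contrast may be available at little cost, but the plan gives it no part in the primary result.

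**Working it through.** **Plan's own figure.** There is no power calculation to reproduce. The sample size adds up: 40 + 10 = 50.

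**Intervals, from Randomization and the primary definition.**
- Active-first: baseline → 5 minutes of Stimulator A.
- Sham-first: baseline → sham period with its measurements → swap → 5 minutes of Stimulator B.

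Without the timing table the sham period's length is unknown, but Stimulator B follows Stimulator A, so the intervals cannot be equal.

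**Expected change (positive = pain relief).** Active-first mean = d + p1. Sham-first mean = d + p2. Pooled mean = (1 − f)(d + p1) + f(d + p2) = d + p1 + f(p2 − p1). Here p1 is the cost of having no comparator, and f(p2 − p1) the cost of unequal intervals. Pooling is inferred from the single end point definition.

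**Size of the interval part.** For p2 − p1 of 0.5 to 1 point: 0.25 to 0.5 at f = 1/2. Over f = 1/3 to 2/3: from 0.5 × 1/3 = 0.17 to 1 × 2/3 = 0.67. The sign follows p2 − p1.

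**Total error of the pooled change.** Assumed: n = 40, 1:1, SD 2.2 at each time, correlation 0.5. The change SD is 2.2 × √(2 × 0.5) = 2.2, so SE = 2.2/√40 = 0.348. Root-mean-square error = √(bias² + 0.348²).

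| p1, p2 | No comparator: p1 | Intervals: (p2 − p1)/2 | Total bias | Root-mean-square error |
|---|---|---|---|---|
| 0, 0.5 | 0 | 0.25 | 0.25 | 0.43 |
| 0.5, 0.5 | 0.5 | 0 | 0.5 | 0.61 |
| 0.5, 1 | 0.5 | 0.25 | 0.75 | 0.83 |
| 1, 1 | 1 | 0 | 1.0 | 1.06 |
| 0.5, −0.5 | 0.5 | −0.5 | 0 | 0.35 |

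In the second and fourth rows none of the bias comes from the unequal intervals; in the last row the two parts cancel. Reversing both signs in any row reverses the bias.

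**Stimulator A comparison, adjusted for baseline, 20 v 20, same assumptions.** SE = 2.2 × √(1 − 0.5²) × √(1/20 + 1/20) = 0.602, and 0.602 × √(37/36) = 0.611 with the small-sample term. The 95% CI half-width is 2.03 × 0.611 ≈ 1.2 points (0.84 to 1.7 for SD 1.5 to 3.0). For a true effect of 1 point, the 10th to 90th percentiles of the estimate are 1 ± 1.28 × 0.611, or 0.22 to 1.78.

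**Which has the smaller error?** If the non-specific response is equal under both units, the contrast is unbiased and does better once the pooled bias exceeds √(0.611² − 0.348²) = 0.50 points (0.34 to 0.69 for SD 1.5 to 3.0). If it differs by an assumed 0.5 points, the contrast's error is √(0.611² + 0.5²) = 0.79, and the break-even moves to √(0.79² − 0.348²) = 0.71.

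**Can the data show p1 = p2?** The sequence difference in the primary change has SE 2.2 × √(1/20 + 1/20) = 0.70 and a 95% half-width of 1.41. Power is about 29% for a difference of 1 point and 11% for 0.5. A non-significant difference would say little.

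**The case against.** The strongest case on the other side has four parts.

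- **The plan does not claim a sham-controlled effect.** It calls itself a feasibility study and says only which change it will treat as primary. This stands. A reader might infer that the plan presents the pooled change as the device effect, but it does not say so. The concern is with how the number could be used later.
- **The unequal intervals may matter little.** The sham period may be short, and in several scenarios all or most of the bias comes from p1. This also stands. A reader might infer that interval mixing is the main source of bias, and the documents do not support that.
- **The randomized contrast is not clean.** The sham delivers no current, while correct lead placement is confirmed before surgery by a paresthesia the subject reports. Subjects may therefore recognize the active unit, and unequal analgesic use before the score would also affect the contrast. This stands and has to be stated with the result.
- **Replacing the primary would trade bias for variance.** With about 20 v 20, the contrast has the larger error when non-specific change is small or of mixed sign, and may have when the response differs between units. A reader might infer that the Stimulator A comparison should displace the stated primary. The documents give no SD, p1 or p2 from which to decide that, so it does not follow.

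What does not stand is the feasibility label as a complete answer: the plan also gives the data a role in powering later trials.

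**Conclusion.** The point holds as a matter of structure. The primary change has no comparator, its interval depends on the randomized sequence, and no handling by sequence is stated. It cannot by itself be read as the effect of the device over sham.

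Its size is not known. A reader might infer that the primary result will overstate benefit. The documents do not support that: non-specific change could lower or raise pain, and total bias at 1:1, (p1 + p2)/2, can be zero. The illustrative totals of 0.25 to 1.0 points rest on assumed drifts; the standard errors rest on an assumed SD of 2.2, a correlation held at 0.5 and 1:1 allocation. A local anesthetic bolus between baseline and first active stimulation is permitted in those with a catheter, but nothing indicates how often it would happen.

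The plan should address this before the estimate is passed to later trials. It does not invalidate the stated primary as a proof-of-concept measure.

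**What to change.** 1. Keep the stated change as the proof-of-concept primary, and report it separately by sequence as well as pooled. Do not describe the pooled change as the device effect.
2. Tabulate by sequence the recovery-room analgesics already recorded and any catheter bolus, split at the time of baseline if times are available. Do not use a non-significant sequence difference to justify pooling.
3. Add the randomized Stimulator A comparison: active versus sham at 5 minutes, adjusted for baseline pain, with its 95% CI. First confirm from the timing table that sham Stimulator A is scored at 5 minutes.
4. Support any device-versus-sham statement with that comparison, and give later trial planning both estimates with their CIs.
5. State the limit: the sham gives no current, so subjects may tell the units apart and the contrast may retain some non-specific response.

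**Cost.** Wording and analysis only, if the 5-minute sham score exists; otherwise the contrast needs that score to be collected. No treatment or clinical rule changes. The price is imprecision: the added contrast may be too wide to settle much alone, which is tolerable in a study that does not present itself as definitive.
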